9.2.4.6 Data Collection

IMS will coordinate data collection with each site. At study initiation (Baseline, D0), patients will be asked to provide their written informed consent. After signing consent, the patients' questionnaires as recorded will be collected. At Week 12 and 24 time-

points, the patients' questionnaires will be collected before them visiting their physicians. There will be a study coordinator or study nurse at each site to monitor the process. The study coordinator/nurse will collect the record of questionnaires directly. Physicians will not see the contents patients entered. The study coordinator/nurse will check to ensure all the forms are filled-in correctly.

In addition, physicians will also be asked to complete a clinical CRF in paper form based on the patient's medical records at baseline, 12 weeks, and 24 weeks. The CRF completed by physicians will be returned to the study coordinator/nurse at each site as well.

All data will be collected by the study coordinator/nurse at each site and returned directly to IMS. The data collection time is expected to be 10-13 months.

All patient and clinician data will be handled preserving confidentiality.

9.2.4.7 Study Documents

Clinical case report form (CRF)

The clinical CRF will document the patient's current status (moderate, severe RA), Disease Activity Score in 28 joints (DAS28), prior and current treatments and other relevant clinical and demographic data to be used in segmenting the population during analysis.

To calculate the DAS28 the physician or specialist nurse will:

1. Count the number of swollen joints (out of the 28)
2. Count the number of tender joints (out of the 28)
3. Record the blood test data of erythrocyte sedimentation rate (ESR) or C reactive protein (CRP) using the latest measurement in the medical records
4. Record the 'global assessment of health' of patients, which will be indicated by marking a 10 cm line between very good and very bad

The physician or specialist nurse will then mark each component score on the CRF and the DAS28 score if calculated (an online scoring calculator for the DAS28 can be found at [REDACTED])

The DAS28 will be scored using the following formula:

$$\text{DAS28 ESR} = 0.56 * \text{sqrt}(\text{tender28}) + 0.28 * \text{sqrt}(\text{swollen28}) + 0.70 * \ln(\text{ESR}) + 0.014 * (\text{Global assessment of Health in cm})$$

$$\text{DAS28 CRP} = 0.56 * \text{sqrt}(\text{tender28}) + 0.28 * \text{sqrt}(\text{swollen28}) + 0.36 * \ln(\text{CRP}) + 0.014 * (\text{Global assessment of Health in cm}) + 0.96$$

DAS28 scores will be interpreted using the following categorization:

- Remission: $DAS28 \leq 2.6$
- Low Disease activity: $2.6 < DAS28 \leq 3.2$
- Moderate Disease Activity: $3.2 < DAS28 \leq 5.1$
- High Disease Activity: $DAS28 > 5.1$

The full CRF is presented in Appendix C.

PRO questionnaires

The following PRO questionnaires will be included in the patient questionnaire packet.

Health Assessment Questionnaire Disability Index (HAQ DI)

The HAQ DI is a patient-reported questionnaire to assess functioning impacted by RA. It includes the categories of dressing and grooming, arising, eating, walking, hygiene, reach, grip and common daily activities. It asks patients about the amount of difficulty they experience in these activities as well as the use of aids and/or devices. The HAQ also has a numeric rating scale (NRS) (13) to assess pain on a scale from 0 to 10. Self-administered by the patient, the completion time is approximately 3-4 minutes. The full version of HAQ DI is presented in Appendix D.

Short Form (36) Health Survey (SF-36)

The SF-36 is a patient-reported questionnaire of patient health-related QoL. It measures generic health concepts relevant across age, disease, and treatment groups. There are 36 items in total and the recall period is the last 4 weeks. The SF-36 consists of eight scaled scores, which are the weighted sums of the questions in their section. Each scale is directly transformed into a 0-100 scale. Completion time for the SF-36 is approximately 10 minutes. The full version of SF-36 is presented in Appendix E.

EuroQol 5 dimension, 3 level quality of life questionnaire (EQ-5D-3L)

The EQ-5D-3L measures the patient's overall health state in a descriptive system of health-related QoL states consisting of five dimensions (mobility, self-care, usual activities, pain/discomfort, and anxiety/depression) each of which can take one of three responses. The responses record three levels of severity ('no problems', 'some problems', and 'extreme problems') within a particular EQ-5D-3L dimension (14, 15). In addition, a VAS rates current health state between 0-100. The EQ-5D-3L results can be converted to health utility scores. Completion time for the EQ-5D-3L is approximately 2-3 minutes. The full version of EQ-5D-3L is presented in Appendix F.

Work Productivity and Activity Impairment (WPAI)

The WPAI is a patient-reported questionnaire to measure work and activity impairment during the past seven days. It determines employment status, hours missed from work due to the disease (i.e. RA), hours missed from work for other reasons, hours actually worked, the degree to which the disease affected work productivity while at work and the degree to which the disease affected activities outside of work. Additional questions around employment status will be incorporated into the survey. The completion time for the WPAI is approximately 2-5 minutes. The full version of WPAI is presented in Appendix G.

All of the above questionnaires will use the validated Chinese version.

Patient Global Impression of Change (PGIC)

The PGIC measures the patient's perceptions of changes in their disease. It consists of one question asking about the change in their condition; for this study, the base will be "since you initiated your adalimumab treatment". The completion time for the PGIC is less than 1 minute. The full version of PGIC is presented in Appendix H.

Patient Treatment Satisfaction Questions

The patient treatment satisfaction questions were developed de novo for this study and are not considered "validated" questions. Self-administered by the patient, the completion time for the patient treatment satisfaction questions is approximately 1-2 minutes. The full version of patient treatment satisfaction questions are presented in Appendix I.

Healthcare Resource Utilization (HCRU) Questionnaire

The HCRU questionnaire will collect data on the healthcare resources consumed in the prior 3 months, as recall beyond 3 months may be problematic in an older population (16). HCRU collection will include data such as the number of physician visits and to which physician (GP, specialist), Emergency Department visits, hospitalizations, and other drugs as well as devices and aids purchased to assist in their mobility due to RA. The HCRU questionnaire will be part of the patient questionnaire and will be distributed to patients together with the PRO questionnaires (Appendix D to Appendix I). The full HCRU questionnaire is presented in Appendix J.

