Appendix C. Clinical Case Report Form (CRF)

Baseline:

1023259 Real-World Impact of RA
[Site number] - [Participant ID]

Clinician Case Report Form (Baseline)

All of the following information must be completed by the clinician or his/her representative.

Clinician name: _____

Clinician signature: _____

Patient ID	[Site #]	-	[Participant #]		
Today's date	[Day]	/	[Month]	/	[Year]

Please provide the information below.	
1. When was the patient diagnosed with Rheumatoid Arthritis?	[Year]
2. What is the patient's current disease status?	 Moderate  Severe

1023259 Real-World Impact of RA
 -
Site number Participant ID

Please provide the information below.		
3. Please perform a swollen and tender joint examination on your patient using the figure below and record the total number of tender/swollen joints in the appropriate boxes on the right.	 Tender Joint Count	 Swollen Joint Count
If diagnosis is RA:		
4. Please record the most recent Erythrocyte Sedimentation Rate (ESR) (in mm/hour) or C-reactive protein (CRP) (in mg/L) of this patient.	 ESR (mm/hour) Test Date (DD/MM/YYYY): ____/____/_____  CRP (mg/L) Test Date (DD/MM/YYYY): ____/____/_____ 5. Please record the latest DAS28 score*, if calculated	

* For calculation instruction, please refer to study protocol, page 21, clinical case report form (CRF).

1023259 Real-World Impact of RA
[REDACTED]
[REDACTED]
Site number - Participant ID

6. Please check all the comorbidities this patient has currently.

- ₀ No comorbidity
- ₁ Myocardial infarction
- ₂ Congestive heart failure
- ₃ Peripheral vascular disease
- ₄ Cerebrovascular disease
- ₅ Dementia
- ₆ Chronic pulmonary disease
- ₇ Connective tissue disease
- ₈ Ulcer disease
- ₉ Mild liver disease
- ₁₀ Diabetes
- ₁₁ Hemiplegia
- ₁₂ Moderate or severe renal disease
- ₁₃ Diabetes with end-organ damage
- ₁₄ Any tumor
- ₁₅ Leukemia
- ₁₆ Lymphoma
- ₁₇ Moderate or severe liver disease
- ₁₈ Metastatic solid tumor
- ₁₉ AIDS

1023259 Real-World Impact of RA
[REDACTED]
Site number - Participant ID

7. Please check all the prior medications this patient has received for her/his Rheumatoid Arthritis in the last 6 months.
(No response option for biologics is given as the current study recruits only patients with no history of any biologics prior to the study).

Drug Name	Average number of pills per day	Dose strength	Times per month

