All of the following information must be completed by the clinician or his/her representative.

Clinician name: _____

Clinician signature: _____

[figure not shown]
[figure not shown]
Site & participant ID

Today's date: / /

Please provide the information below.		
1. What is the patient's current disease status?	 Moderate	 Severe

1023259 Real-World Impact of RA

100

Please provide the information below.
 
2. Please perform a swollen and tender joint examination on your patient using the figure below and record the total number of tender/swollen joints in the appropriate boxes on the right.
		 	Tender Joint Count	 	Swollen Joint Count

If diagnosis is RA:
 
 
  
 
  
 
					

3. Please record the most recent Erythrocyte Sedimentation Rate (ESR) (in mm/hour) or C-reactive protein (CRP) (in mg/L) of this patient.
			
   ESR (mm/hour)
 
   CRP (mg/L)
		

4. Please record the latest DAS28 score*, if calculated
					

* For calculation instruction, please refer to study protocol, page 21, clinical case report form (CRF).

1023259 Real-World Impact of RA
[Site number] - [Participant ID]

[figure not shown]
5. Please check all the surgeries this patient has received for her/his Rheumatoid Arthritis since the last completed survey.			
 No surgery performed			
 Yes →	Type of Surgery (Please input the number of the list below)	Length of Stay*	Date of surgery (DD/MM/YYYY)
	 1 _____	_____ days	_____/_____/_____
	 2 _____	_____ days	_____/_____/_____
	 3 _____	_____ days	_____/_____/_____
	 4 _____	_____ days	_____/_____/_____
	 5 _____	_____ days	_____/_____/_____
List of common surgeries for rheumatoid arthritis:			

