Appendix K. Early Termination Form

For Physician:

1023259 Real-World Impact of RA

Early Termination Form (Clinician)

All of the following information must be completed by the clinician or his/her representative.

Clinician name: _____

Clinician signature: _____

□ □ □ □ □ □ □

Site & participant ID

Today's date: / /

Please provide the information below.	
1. What is the patient's current disease status?	 Moderate  Severe

1023259 Real-World Impact of RA
[Site number] - [Participant ID]

Please provide the information below.		
2. Please perform a swollen and tender joint examination on your patient using the figure below and record the total number of tender/swollen joints in the appropriate boxes on the right.	  Tender Joint Count	  Swollen Joint Count
If diagnosis is RA:		
3. Please record the most recent Erythrocyte Sedimentation Rate (ESR) (in mm/hour) or C-reactive protein (CRP) (in mg/L) of this patient.	  ESR (mm/hour) Test Date (DD/MM/YYYY): ____/____/_____   CRP (mg/L) Test Date (DD/MM/YYYY): ____/____/_____ 4. Please record the latest DAS28 score*, if calculated	
		

* For calculation instruction, please refer to study protocol, page 21, clinical case report form (CRF).

1023259 Real-World Impact of RA
[REDACTED]
Site number - Participant ID

5. Please check all the surgeries this patient has received for her/his Rheumatoid Arthritis since the last completed survey.

 No surgery performed	 Yes →	Type of Surgery (Please input the number of the list below)	Length of Stay*	Date of surgery (DD/MM/YYYY)
		 1	_____ days	____/____/____
		 2	_____ days	____/____/____
		 3	_____ days	____/____/____
		 4	_____ days	____/____/____
		 5	_____ days	____/____/____

List of common surgeries for rheumatoid arthritis:

1. Arthroscopy
2. Carpal tunnel release
3. Cervical spinal fusion
4. Total knee replacement
5. Total hip replacement
6. Knee arthrodesis (fusion)
7. Hip arthrodesis (fusion)
8. Synovectomy
9. Other: _____

* For day surgeries, please input 0 days.

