 - Age at baseline
 - Age groups
 - Gender at birth
 - Marital status (married, unmarried)
 - Medical plan type
 - ✓ The type of healthcare plan each patient is enrolled in at baseline will be determined, including National/Public insurance, Private insurance, Employer benefits, and Other
- **Clinical characteristics**
 - Initial Diagnosis of Rheumatoid Arthritis (RA)
 - ✓ Year of initial diagnose
 - Initiation of Adalimumab
 - ✓ First time administration (DD/MM/YYYY)
 - ✓ Dosage of first injection (in mg)
 - Disease status of RA
 - ✓ Moderate (defined as Disease Activity Score in 28 Joints (DAS28) between 3.2 and 5.1)
 - ✓ Severe (DAS28>5.1)
 - Erythrocyte sedimentation rate (ESR) (in mm/hour)
 - C reactive protein (CRP) (in mg/L)
 - Disease Activity Score in 28 joints (DAS28)

To calculate the DAS28, the physician or specialist nurse will:

1. Count the number of swollen joints (out of the 28)
2. Count the number of tender joints (out of the 28)
3. Take blood to measure the erythrocyte sedimentation rate (ESR) or C reactive protein (CRP); the latest measurement in the medical records may also be used if a blood draw is not standard for that visit

4. Ask the patient to make a 'global assessment of health' which will be indicated by marking a 10 cm line between very good and very bad

The physician or specialist nurse will then mark each component score on the CRF and the DAS28 score if calculated (an online scoring calculator for the DAS28 can be found at <http://www.das-score.nl/das28/DAScalculators/dascalculators.html>).

The DAS28 will be scored using the following formula:

$$\text{DAS28} = 0.56 * \text{sqrt}(\text{tender28}) + 0.28 * \text{sqrt}(\text{swollen28}) + 0.70 * \ln(\text{ESR or CRP}) + 0.014 * (\text{Global assessment of Health})$$

DAS28 scores will be interpreted using the following categorization:

- ✓ Remission: DAS28 \leq 2.6
- ✓ Low Disease Activity: $2.6 < \text{DAS28} \leq 3.2$
- ✓ Moderate Disease Activity: $3.2 < \text{DAS28} \leq 5.1$
- ✓ High Disease Activity: DAS28 > 5.1

– comorbidities

- ✓ Myocardial infarction
- ✓ Congestive heart failure
- ✓ Peripheral vascular disease
- ✓ Cerebrovascular disease
- ✓ Dementia
- ✓ Chronic pulmonary disease
- ✓ Connective tissue disease
- ✓ Ulcer disease
- ✓ Mild liver disease
- ✓ Diabetes
- ✓ Hemiplegia
- ✓ Moderate or severe renal disease
- ✓ Diabetes with end-organ damage
- ✓ Any tumor
- ✓ Leukemia
- ✓ Lymphoma
- ✓ Moderate or severe liver disease
- ✓ Metastatic solid tumor
- ✓ AIDS

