5.5 Analysis Plan for Exploratory Objectives

- Excel Table 7 describes the change in 4 patient satisfaction questions at weeks 12 and 24 after the initiation of adalimumab, in those patients continuing on adalimumab (observed population). These changes will be summarized as number and percentage of each response and compared with Wilcoxon signed rank test shown by p-value1. Satisfaction will also be dichotomized and analyzed over time with Cochran-Armitage test for trends shown by p-value2 in the table.
- Excel Table 8 summarizes the patients' global impression of change in RA at weeks 12 and 24 after the initiation of adalimumab, in those patients continuing on adalimumab (as observed population). Each response (very much better, much better, a little better, no change, a little worse, much worse, and very much worse) will be summarized as number and percentage.
- Descriptive statistics will be presented for post-index overall RA related direct healthcare resource utilization (Excel Table 9)
 - Consultations/visits to healthcare professionals for treatment of RA (number of patients with ≥ 1 visit; categorized by the treatment department listed in 3.5.4)
 - Procedures received when visiting the healthcare professional(s) for treatment of RA (number of patients with ≥ 1 procedure; categories listed in 3.5.4)
 - surgeries received when visiting the healthcare professional(s) for treatment of RA (number of patients with ≥ 1 surgery; categories listed in 3.5.4)
 - Hospitalizations in relation to RA (number of patients with ≥ 1 admission)
 - Length of stay in days (mean, SD, median)
 - Concomitant medications taken for RA (number of patients with ≥ 1 medication; categories listed in 3.5.4))
- Associations between disease severity (measured by DAS28) and PROs (HAQ DI score, SF-36 domain scales, EQ-5D-3L index, WPAI outcomes) will be analyzed using the bivariate linear regression model (Excel Table 10.1). Separate models will be estimated to identify the association between DAS28 and each of the PROs.
- Additionally, in Excel Table 10.2, separate bivariate liner regression models will be estimated to identify the association between change in DAS28 and change in each of the PROs at 12 and 24 weeks after baseline respectively.

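### The Week 12/24 form takes an undated ESR/CRP and shows no patient-global item, so follow-up DAS28 in the exploratory analyses cannot be fully checked or recomputed

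*Protocol*

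**What the plan says.** Protocol 9.2.4.7 gives the source of the laboratory component of DAS28: "Record the blood test data of erythrocyte sedimentation rate (ESR) or C reactive protein (CRP) using the latest measurement in the medical records". SAP 3.5.2 is narrower. It has blood taken, but adds that "the latest measurement in the medical records may also be used if a blood draw is not standard for that visit". Neither text sets a maximum age for the value.

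The Week 12/24 clinician form (Protocol Appendix C) asks: "Please record the most recent Erythrocyte Sedimentation Rate (ESR) (in mm/hour) or C-reactive protein (CRP) (in mg/L) of this patient". No test date appears beside that item. The baseline form does carry one ("ESR (mm/hour) Test Date (DD/MM/YYYY"), and so does the early-termination form in Appendix K ("Test Date (DD/MM/YYYY").

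Protocol 9.2.4.7 also requires a global assessment on a 10 cm line and says that the assessor "will then mark each component score on the CRF and the DAS28 score if calculated". The form's own item for the total reads "Please record the latest DAS28 score*, if calculated".

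The main use of follow-up DAS28 is in SAP 5.5, Table 10.2, where "separate bivariate liner regression models will be estimated to identify the association between change in DAS28 and change in each of the PROs" at Weeks 12 and 24.

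**The concern.** Change in DAS28 is the predictor in Table 10.2. If the follow-up score contains a laboratory value drawn before treatment, the laboratory part of the change is zero by construction, whatever happened to the patient. The situation is foreseeable. Protocol 12.5 says the study imposes no laboratory tests, and 9.2.4.6 has physicians complete the form from medical records. The date that would reveal the problem is missing on the one scheduled form where it matters most.

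The second gap is reconstruction. With no global score on file and the total optional, an analyst cannot compute the full formula for a patient whose site did not. Protocol 9.7.9 and SAP 3.5.5 allow no imputation beyond questionnaire items and certain dates, so that patient would leave the DAS28 analyses.

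**Working it through.** The plan states no figure that this point depends on, so there is nothing to reproduce first.

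**1. Forms side by side.**

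| Item | Baseline | Week 12/24 | Early termination |
|---|---|---|---|
| Joint counts | item 3 | item 2 | item 2 |
| ESR or CRP | item 4 | item 3 | item 3 |
| Test date | yes | none shown | yes |
| Patient global | none shown | none shown | none shown |
| DAS28 total, optional | item 5 | item 4 | item 4 |
| Status options | Moderate, Severe | Moderate, Severe | Moderate, Severe |

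Item numbers run without a break (1 to 11, 1 to 8, 1 to 8), so no numbered global item has dropped out of the text.

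**2. Size of a carried-over value.** The protocol's laboratory terms are 0.70 × ln(ESR) and 0.36 × ln(CRP). The hidden improvement is the coefficient × ln(old value / current value). The laboratory values are my assumptions; the documents give none.

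- ESR 40 to 30, 20 or 10 mm/h: 0.70 × ln(40/30) = 0.20; 0.70 × ln(40/20) = 0.49; 0.70 × ln(40/10) = 0.97.
- CRP 20 to 10, 5 or 2 mg/L: 0.36 × ln(20/10) = 0.25; 0.36 × ln(20/5) = 0.50; 0.36 × ln(20/2) = 0.83.

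**3. One assumed patient** (tender joints 10 to 3, swollen 8 to 2, ESR 40 to 20, global 6 to 3 cm).

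- Baseline: 0.56√10 + 0.28√8 + 0.70 ln 40 + 0.014 × 6 = 5.23.
- Follow-up, current ESR: 0.56√3 + 0.28√2 + 0.70 ln 20 + 0.014 × 3 = 3.50; change −1.72.
- Follow-up, old ESR: 3.50 + 0.49 = 3.99; change −1.24.
- Share of the change kept: 1.24/1.72 = 72%.

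**4. Mean effect by share affected** (ESR 40 to 20 in everyone). At 10%, 25%, 50% and 100% of patients, the mean change shrinks by share × 0.485 = 0.05, 0.12, 0.24 and 0.49.

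**5. Missing global.** Scored in cm, as the protocol writes it, the term is worth at most 0.014 × 10 = 0.14. Scored 0 to 100 it would be worth up to 1.4; the SAP formula states no unit. For the same patient, in cm, leaving it out at both visits gives a change of −1.68, and leaving it out at follow-up only gives −1.77. The error goes either way.

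**6. Effect on the Table 10.2 slope.**

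- A constant shift of 0.49 in every patient leaves the slope unchanged.
- Proportional shrinkage to 72% steepens it by 1/0.72 = 1.39.
- If half the patients carry the 0.485 error, unrelated to response, the predictor gains variance 0.485² × 0.5 × 0.5 = 0.059. The slope is then multiplied by V/(V + 0.059), where V is the true variance of DAS28 change, which the documents do not give. That flattens it.

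**7. Reach.** The primary paired t-test uses HAQ DI only. Its sensitivity ANOVA and the Table 11 models use baseline severity. SAP 5.2 tabulates DAS28 categories at baseline only. That leaves Table 10.2, and Table 10.1 if follow-up values enter it; SAP 5.5 does not say which visits it uses.

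**The case against.** A reader might infer that all these gaps together bias disease-activity change toward no change. The documents do not support that. Only an old laboratory value points that way, and only if it predates the response; joint counts are still examined at the visit. The missing global has no fixed direction, and step 6 shows that the slope has none either.

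A reader might also infer that the status item corrupts the severity analyses, since a patient at or below 3.2 has no valid box. The gap on the form is real, but SAP 5.5 measures severity by DAS28, and no listed table uses the follow-up box or follow-up activity categories.

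Other objections stand in part:

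- A reused baseline value would usually equal the one on the baseline form, so an equality check would catch some cases. It would miss an old value drawn after baseline, or a switch between ESR and CRP, and would flag chance ties. Neither document names such a check.
- With the global in cm, the remaining components recover DAS28 to within 0.14. That holds only if the unit is cm.
- Routine laboratory data are inherent in a non-interventional study. That explains the fallback, not the missing date.
- A 10 cm line is a graphic, and the forms were read by a program. The absence of the date and global fields must be confirmed on the original forms. The same reading does show date lines on the other two forms.

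**Conclusion.** The point holds, with limited reach. As written, the plan lets an ESR or CRP of any age enter the follow-up DAS28, and the Week 12/24 form gives no reliable way to see it. Each affected patient's improvement would be understated by about half a point under the assumed falls (range 0.20 to 0.97 across those tried). The share of patients affected is unknown, so the effect on the mean cannot be fixed: 0.05 points at 10% affected, 0.24 at 50%.

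Separately, the protocol says each component is marked on the form, yet no clinician form shows a place for the global. The score therefore cannot be fully recomputed or checked where the site did not calculate it.

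The consequence is confined to the exploratory DAS28 associations, whose slopes may be distorted either way. The primary HAQ DI result is unaffected. All sizes rest on assumed laboratory values and the protocol's formula. The SAP's single formula puts 0.70 on ln(CRP) and omits the 0.96 constant; under it, CRP 20 to 5 would hide 0.70 × ln 4 = 0.97. That discrepancy is a separate matter, but the two formulas must be reconciled before any DAS28 is derived.

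**What to change.** - **Forms.** Add the ESR/CRP test date to the Week 12/24 form, and a global-assessment field with its unit to all three clinician forms. If the forms are already complete, retrieve laboratory dates from the medical records by query. That is likely, since data collection was planned to end in January 2017 and the SAP cites table shells dated January 2018.
- **Status.** Derive it from DAS28 rather than from the two-option box.
- **SAP 3.5.2.** State that a follow-up DAS28 uses only an ESR or CRP dated after the first dose and within a prespecified window of the visit; otherwise it is missing. The ±7 days in Protocol Table 1 is one candidate, to be settled before the data are examined.
- **Reporting.** Give the share of follow-up values outside the window or undated, and show Table 10.2 with and without them. State which visits feed Table 10.1.

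The cost is a few form fields or one round of queries, one derivation rule and one extra table. The downside is that some follow-up DAS28 values become missing, and these may fall mainly on patients without routine blood draws. Showing both versions of Table 10.2 keeps that visible.

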Subjects that initially screen fail for the study may be permitted to re-screen following re-consent. All screening procedures with the possible exceptions noted below will be repeated. The subject must meet all inclusion and none of the exclusion criteria at the time of re-screening in order to qualify for the study. There is no minimum period of time a subject must wait to re-screen for the study. If the subject had a complete record of eligible criteria including a PPD test (or equivalent), or Interferon-Gamma Release Assay (IGRA; QuantiFERON-TB Gold In-Tube test or T-SPOT TB test), Chest x-ray (if applicable) and ECG no more than 3 months (90 days) have passed, these data will not be required to be repeatedly collected for re-screening. As appropriate, sites are encouraged to contact the AbbVie Medical Monitor to confirm if subjects should or should not be re-screened.

9.2.1 Inclusion Criteria:

Patients meeting all of the following inclusion criteria at baseline will be included:

1. Subject has a diagnosis of RA as defined by the 1987 revised ACR classification criteria and/or the ACR/ the European League against Rheumatism (EULAR) 2010 classification criteria (any duration since diagnosis)
2. Male or female subjects ≥ 18 years of age (local definition according to adalimumab label) who is in compliance with eligibility for adalimumab based on the local label
3. Patients with moderate to severe RA defined as DAS28 (ESR) or DAS28 (CRP) > 3.2

4. Biologically treatment naïve and initiated adalimumab at baseline visit
5. Availability of clinical data of the previous 12 weeks prior to baseline
6. Ability to self-complete patient questionnaires
7. Subject must be able and willing to provide written informed consent and comply with the requirements of this study protocol

Additional Inclusion Criteria

8. Female subjects who are either not of childbearing potential, defined as postmenopausal for at least 1 year or surgically sterile (bilateral tubal ligation, bilateral oophorectomy and/or hysterectomy) or are of childbearing potential and are practicing an approved method of birth control throughout the study and for 150 days after the Week 24 dosing or the last dose of adalimumab.

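### Both DAS28 formulas enter the global assessment in cm with weight 0.014, so it adds at most 0.14; unit, weight and cut-offs must be reconciled across protocol, SAP and CRF

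*Protocol*

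**What the plan says.** Protocol 9.2.4.7 lists four DAS28 components. The fourth is the patient's global assessment, "which will be indicated by marking a 10 cm line between very good and very bad". The section then states: "The DAS28 will be scored using the following formula". It prints an ESR version and a CRP version. In both, the last patient-derived term is 0.014 times the "Global assessment of Health in cm". The same section sets the activity bands at 2.6, 3.2 and 5.1 and also points to an online calculator.

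SAP 3.5.2 repeats the 10 cm line, the weight 0.014, the bands and the calculator, but gives no unit for the global assessment. Neither document mentions mm or a 0-100 range for this item.

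The CRF (Protocol Appendix C) asks for a DAS28 score only if one was calculated, with the footnote "For calculation instruction, please refer to study protocol, page 21, clinical case report form (CRF". It also has a separate box in which the clinician ticks moderate or severe disease.

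DAS28 is used in these places:
- Entry: "Patients with moderate to severe RA defined as DAS28 (ESR) or DAS28 (CRP) > 3.2" (Protocol 9.2.1, criterion 3).
- Definition of moderate and severe disease: SAP 3.5.2, cut at 5.1.
- Baseline table: SAP 5.2, Table 2.
- Association models: SAP 5.5, Tables 10.1 and 10.2.

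Baseline disease severity is also the adjustment factor in the sensitivity ANOVAs (Protocol 9.7.4 and 9.7.5, SAP 5.3), a subgroup factor (Protocol 9.7.3) and a modifier in Table 11 (SAP 5.5).

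**The concern.** With a 10 cm line, a reading in cm and a weight of 0.014, the whole distance from very good to very bad health moves the index by 0.14. One of the four components that sites are told to collect then has almost no influence on the score. This suggests a mismatch between unit and weight.

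If so, scores from the printed formula lie below the scale for which the cut-offs were meant, and always in the same direction. Some patients could miss entry, some with high activity could be labelled moderate, and patient-perceived improvement would nearly vanish from the DAS28 change that Table 10.2 relates to change in the PROs. Because the SAP gives no unit and a calculator is also offered, two scales could also sit side by side in one dataset.

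**Working it through.** The plan states no figure that depends on the DAS28 formula, so there is none to reproduce. The check is arithmetic on the printed formulas.

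**Inputs.** From Protocol 9.2.4.7: weight 0.014 per cm; line 0 to 10 cm; 0.56 × √tender; 0.28 × √swollen; 0.70 × ln(ESR), or 0.36 × ln(CRP) + 0.96; cut-offs 3.2 and 5.1. Assumption not printed in the documents: the weight and cut-offs belong to the same line read 0-100 (mm).

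**Step 1: range of the global term, from the documents alone.**
- As printed: 0.014 × 10 = 0.14.
- First tender joint: 0.56 × √1 = 0.56, and 0.14 / 0.56 = one quarter.
- Largest tender-joint term: 0.56 × √28 = 2.96. Largest swollen-joint term: 0.28 × √28 = 1.48. ESR term at 30 mm/h: 0.70 × ln 30 = 2.38.
- An improvement in the global mark from 7 to 3 cm changes DAS28 by 0.014 × 4 = 0.056.

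**Step 2: shortfall under the 0-100 assumption.** The term would run to 0.014 × 100 = 1.40. For a mark of G cm the shortfall is 0.014 × (10G − G) = 0.126 × G. The moderate band is 5.1 − 3.2 = 1.9 wide.

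| Mark (cm) | Shortfall | 0-100 scores that fall to 3.2 or below | 0-100 scores classed moderate, not high |
|---|---|---|---|
| 3 | 0.38 | above 3.2, up to 3.58 | above 5.1, up to 5.48 |
| 5 | 0.63 | above 3.2, up to 3.83 | above 5.1, up to 5.73 |
| 7 | 0.88 | above 3.2, up to 4.08 | above 5.1, up to 5.98 |
| 10 | 1.26 | above 3.2, up to 4.46 | above 5.1, up to 6.36 |

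The same improvement from 7 to 3 cm would change DAS28 by 0.014 × 40 = 0.56.

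**Step 3: illustrative patients with mid-scale marks.**

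| Version | Tender | Swollen | ESR or CRP | Mark | Printed (cm) | Read 0-100 |
|---|---|---|---|---|---|---|
| ESR | 1 | 1 | 20 | 6 cm | 3.02, not eligible | 3.78, eligible |
| CRP | 3 | 2 | 5 | 6 cm | 2.99, not eligible | 3.75, eligible |
| ESR | 8 | 6 | 35 | 7 cm | 4.86, moderate | 5.74, high |
| CRP | 8 | 6 | 15 | 7 cm | 4.30, moderate | 5.18, high |

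First row in full: 0.56 + 0.28 + 0.70 × ln 20 (2.10) = 2.94; adding 0.014 × 6 = 0.08 gives 3.02, and adding 0.014 × 60 = 0.84 gives 3.78.

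**Step 4: the primary analysis.** It is an unadjusted paired t-test on HAQ DI. With 100 × 0.9 = 90 patients (noncentral t), power is 97.6% for a mean of −0.21 with SD 0.5. For a difference of 0.50 − 0.22 = 0.28 with SD 0.7 it is 96.4%. Both agree with the stated figure of at least 95%, and neither uses DAS28.

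**The case against.** The strongest objection is that the 0-100 reading is not in the documents. That is correct. The near-zero influence of the item makes a unit slip plausible but does not prove which unit was meant. The 0.14 ceiling stands without the assumption; every shortfall figure depends on it.

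The harm is also conditional. It arises only where a site calculates by the printed formula. The CRF footnote refers to a protocol section that contains both the formula and the calculator. A reader might infer that the two routes must give different scores, but the calculator's input unit cannot be seen. They may differ; the documents do not show that they do.

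A reader might likewise infer that the severity factor is wrong throughout the analysis. SAP 3.5.2 defines disease status by DAS28 bands, but the CRF also collects the clinician's moderate/severe tick. Neither document says which of the two supplies baseline disease severity in the ANOVA.

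Finally, central recalculation may not be possible. Protocol 9.2.4.7 says each component is marked on the CRF, but the form as extracted shows joint counts, ESR or CRP and the DAS28 score, with no visible field for the global mark. Figures are missing from the text, so absence is not established. This limits the remedy without removing the defect.

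**Conclusion.** The point holds as a defect in the scoring rule. As printed, the global assessment adds at most 0.14 to DAS28, and nothing in either document corrects or explains this. The SAP leaves the unit open.

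Assuming that the weight and cut-offs belong to a 0-100 reading, the printed formula understates DAS28 by 0.126 per cm, which is 0.63 to 0.88 for marks of 5 to 7 cm. The 1.26 is an upper bound, reached only at a mark of exactly 10 cm, and should not be read as a typical error. Under that assumption the error is never upward: it can exclude patients or move them from high to moderate, but cannot wrongly admit anyone.

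Where the formula is used, the consequences reach entry, Tables 2, 10.1 and 10.2, and, if severity is derived from DAS28, the sensitivity ANOVAs, the severity subgroups and Table 11. A reader might go further and doubt the primary result. The documents do not support that: the primary test and its power contain no DAS28 term. DAS28 touches the primary endpoint only through who is enrolled.

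**What to change.** 1. Reconcile unit, weight and cut-offs in both formulas of Protocol 9.2.4.7 and in SAP 3.5.2, and state one unit in all three places: 0-100 mm, once verified against the source of the index.
2. In the same edit, resolve the separate mismatch for CRP. The SAP applies 0.70 × ln to either marker with no constant, whereas the protocol's CRP version uses 0.36 × ln(CRP) + 0.96. Correcting the unit alone would leave CRP-based scores unreconciled.
3. For the analysis, derive DAS28 centrally from its components wherever the raw global mark was recorded.
4. Confirm that the CRF captures that mark. Where it does not, record whether the site score came from the formula or the calculator, and flag those scores in the DAS28 tables.
5. State in the SAP whether baseline disease severity comes from the derived DAS28 or from the clinician's tick-box.

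Cost: wording changes in the protocol and SAP, one derivation in the analysis program, and possibly one CRF field. Some patients may change severity stratum.
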